Any adverse events observed from the signing of the informed consent but prior to initial navitoclax administration will be reported, as serious or non-serious adverse events, if considered by the investigator to be causally related to study-required procedures.

At each visit, the subject's medical history will be reviewed and any changes from baseline will be recorded on the adverse event eCRF.

All medications (prescription or over-the-counter, including vitamins and/or herbal supplements) will be recorded beginning with the Screening Visit and continuing until 30 days following the last dose of study drug.

Bone Marrow and Cytogenetic Assessment

A bone marrow biopsy must be collected along with a bone marrow aspirate (provided the aspirate sample can be collected) and evaluated locally during Screening and as outlined in Appendix C. Cytogenetic analysis should be evaluated at Screening for determination of risk stratification. If cytogenetic analysis was not performed at Screening, a historical result may be utilized for risk stratification determination provided it was obtained within 6 months of Screening and a new therapy was not initiated between the time of collection and Screening. This evaluation will include staining for fibrosis and staining for reticulin grading and cytogenetics. Cytogenetic results from peripheral blood specimen with an adequate number of malignant cells is satisfactory for analysis. Should peripheral blood yield an insufficient number of metaphases analyzed by chromosomal banding analysis (<10), a Fluorescence In Situ Hybridization (FISH) panel for MPN may be used to determine whether the subject has an "unfavorable karyotype," as defined by the DIPSS+, as long as presence of all chromosome abnormalities are assessed: +8; -7/-7q; i(17q); -5/-5q; 12p-; inv(3); 11q23 rearrangement; 20q-; 13q- and 9.

Historical results from bone marrow samples cannot replace the mandatory bone marrow biopsy and aspirate samples obtained and analyzed at Screening.

Bone marrow biopsies and aspirates performed as standard of care during study participation should also be captured on the eCRF. An adequate bone marrow aspirate, if available, will be collected for predictive biomarker assessments.

After 96 weeks of treatment, bone marrow sampling is only necessary to be performed if disease progression is suspected, or at the discretion of the investigator.

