#### Definition of First Date of and Last Date of Study Treatment

First date of study treatment is the date of the first dose of navitoclax. Last date of study treatment is the date of the last dose of navitoclax.

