#### 7.5 Prior and Concomitant Medications

Prior and concomitant medications including prior treatments for MF and preceding treatment for polycythemia vera or essential thrombocythemia prior to developing secondary MF will be summarized by generic name. A prior medication is defined as any medication taken before the first date of study treatment.

A concomitant medication is defined as any medication that started before or after the first date of study treatment and continued to be taken after the first date of study treatment, but not after the last date of study treatment. The number and percentage of subjects taking medications will be summarized by generic drug name based on the World Health Organization (WHO) Drug Dictionary for both prior and concomitant medications.

Subjects who report the use of medications more than one time will be counted only once in the summary of any prior or concomitant medication. Subjects reporting two or more uses of the same medication will be counted only once in the total for the associated generic drug name.

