# 9.2.1 Treatment-Emergent Adverse Events

[figure not shown]
Treatment-emergent AEs (TEAE) are defined as any AE with the onset that is on or after the first dose of navitoclax until 30 days after the last date of study drug. Events where the onset date is the same as the study drug start date are assumed to be treatment emergent. If an incomplete or missing onset date was collected for an AE, the AE will be assumed to be treatment-emergent unless there is evidence to the contrary (e.g., the AE end date was prior to the date of the first dose of study drug). All TEAEs will be summarized overall, as well as by primary MedDRA SOC and PT. The SOCs will be presented in alphabetical order, and the PTs will be presented in alphabetical order within each SOC.

The number and percentage of subjects experiencing TEAEs will be summarized.

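### SAP 7.5, read literally, leaves a drug that was used during treatment and continued past the last navitoclax dose out of the concomitant-medication table

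*Protocol*

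**What the plan says.** SAP 7.5 gives two definitions. The first reads: "A prior medication is defined as any medication taken before the first date of study treatment". It does not require that the drug had stopped by then. The second covers "any medication that started before or after the first date of study treatment" that also "continued to be taken after the first date of study treatment, but not after the last date of study treatment". Both feed one kind of summary: the number and percentage of subjects taking each drug "will be summarized by generic drug name based on the World Health Organization (WHO) Drug Dictionary for both prior and concomitant medications".

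SAP 7.1 fixes the dates. The first date of study treatment is the first navitoclax dose, and for the other end: "Last date of study treatment is the date of the last dose of navitoclax".

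On collection, Protocol 5.3.1.1 (Adverse Event and Concomitant Medication Assessment) says all medications "will be recorded beginning with the Screening Visit and continuing until 30 days following the last dose of study drug". Protocol 5.2.4 requires start and end dates for each. For comparison, SAP 9.2.1 counts adverse events as treatment-emergent "until 30 days after the last date of study drug".

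**The concern.** A concomitant-medication table should show what subjects took while on study treatment. In the SAP 7.5 sentence, the limit at the last date of study treatment attaches to continued use of the drug, not to its start. A drug taken throughout treatment and for a further week therefore fails the definition because of that week. Long-term medication is the kind most exposed to this.

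Protocol 5.2.4 permits low-dose aspirin, low-molecular-weight heparin, limited NSAID use and colony-stimulating factors. SAP Appendix E lists hemorrhage, neutropenia and serious infection among the safety topics of interest. A reader may turn to the medication table for context on those events, and the SAP plans no other summary of use of these permitted drugs. The subjects lost from the count are those who stopped navitoclax while still needing the drug.

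**Working it through.** There is no sample size, test or interval to reproduce. The check applies SAP 7.5 as written to each possible pattern of use. F is the first and L the last navitoclax dose date (SAP 7.1).

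| Case | Drug started | Last use | Prior | Concomitant, as written | Concomitant, if the limit applies to the start date |
|---|---|---|---|---|---|
| 1 | before F | after F, by L | yes | yes | yes |
| 2 | before F | after L | yes | **no** | yes |
| 3 | after F | by L | no | yes | yes |
| 4 | after F, by L | after L | no | **no** | yes |
| 5 | after L, within 30 days | after L | no | no | no |
| 6 | on F | any | no | **unassigned** | unassigned |

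Cases 2 and 4 are the defect. In case 2 the subject is still visible as a prior user. In case 4 (for example, heparin begun on Day 50 and still running at the last navitoclax dose) the drug is in neither table. Case 6 is a separate gap: the definition covers starts before or after the first date, but not on it. Case 5 is not on-treatment use, so leaving it out is not an error.

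**Size.** For one drug in one cohort, let N be the subjects who used it on treatment and C those among them who stopped navitoclax and kept taking it. Setting case 6 aside:

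- concomitant count as written = N − C
- of the C subjects, those who began before Day 1 remain in the prior table; the others are in neither.

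The documents give neither N nor C. With N assumed to be 10:

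- C = 0: 10 − 0 = 10 counted
- C = 4: 10 − 4 = 6 counted
- C = 8: 10 − 8 = 2 counted
- C = 10: 10 − 10 = 0 counted

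The range runs from no loss to complete loss, and these figures only illustrate the rule. A subject still on navitoclax at the data cut has no last date yet and does not contribute to C. Subjects are counted once per generic name, so one with a second course of the same drug that ended on treatment is still counted.

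**Reach.** The overall-survival rule (SAP 8.5.1.10) lists the start date of a concomitant or post-treatment medicine among the dates used to find when a subject was last known alive. In cases 2 and 4 the drug started no later than L, and the last dose date is in the same list, so the latest date cannot change. Anemia response (SAP 8.4.1.2) has its own rule for erythropoietin and does not refer to SAP 7.5.

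**The case against.** The strongest reply is that the sentence is loosely worded and not a deliberate rule. The sponsor may have meant that a drug must not have *started* after the last date, in which case cases 2 and 4 are counted. SAP 1.0 leaves programming details to a Statistical Programming Plan that is not among the documents, and that plan may implement the sensible version. This stands as a limit on certainty: it cannot be said that the table will undercount. It does not remove the point, because the SAP does not state that meaning and nothing else in SAP 7.5 brings these drugs back.

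The reply is also right that the reach is narrow. The prior table still shows drugs begun before Day 1. Short courses that begin and end on treatment are counted either way. Safety topics come from adverse-event searches (SAP 9.2.5, Appendix E), transfusions have their own summary (SAP 9.2.5.3), and prohibited medication is reported as a protocol deviation (SAP Appendix A).

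Three stronger readings are tempting and are not supported:

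- A reader might infer that the protocol and SAP contradict each other, because recording runs to 30 days after the last dose. Collecting over a longer period than is tabulated is no contradiction.
- A reader might infer that the table must match the 30-day adverse-event window. No document requires that.
- A reader might infer that the cohorts' medication profiles become invalid to compare because cohorts differ in follow-up. The undercount does grow as more subjects stop, and SAP 11.0 allows summaries at different maturities, but no comparison of medication use between cohorts is planned.

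**Conclusion.** The point holds as a defect in one definition. Followed literally, SAP 7.5 excludes on-treatment use of any drug that continues past the last navitoclax dose. Such a drug is shown only as prior if begun before Day 1, and in neither table if begun on treatment. A drug started on Day 1 is unassigned on either reading.

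The loss from continued use equals the number of users who stopped navitoclax but not the drug. Its actual size cannot be derived from the documents. The conclusion assumes that the sentence is programmed as written. If the sponsor's program limits the start date instead, only the Day 1 gap remains.

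The consequence is limited to a descriptive table. No endpoint or safety-topic search is affected, and the individual records, with their dates, are still collected. This is a minor correction, but worth making because the rule as stated gives a wrong count.

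**What to change.** Replace the concomitant-medication sentence in SAP 7.5 with:

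*A concomitant medication is any medication taken on at least one day from the first date through the last date of study treatment, whatever its start date and whether or not it continues afterwards.*

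This settles cases 2 and 4 and covers a Day 1 start. The prior-medication definition can stay, so a drug used both before and during treatment appears in both tables.

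If the sponsor wishes, drugs started within 30 days after the last dose can be flagged separately. That is optional. The protocol needs no change.

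The cost is one SAP sentence and a check of one date condition in the program. The start and end dates it needs are already collected.

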- Cohort 1b only: Subjects that are receiving ruxolitinib at the time of screening, must currently be on a stable dose ≥ 10 mg twice daily of ruxolitinib for ≥ 4 weeks prior to the 1st dose of navitoclax.

Note: Subjects with ruxolitinib dose reductions within 4 weeks prior to study enrollment are considered to be on a stable dose if dose of ruxolitinib if the dose is unchanged for ≥ 2 weeks prior to Day 1 of navitoclax. The current dose must be ≥ 10 mg twice daily. If the dose reduction was due to thrombocytopenia, platelet counts must be confirmed to be stable by a repeat laboratory test.

Cohort 1b only: Subject must not have received treatment with a BET inhibitor or an alternate JAK-2 inhibitor other than ruxolitinib.

Diagnosis and Main Criteria for Inclusion/Exclusion (Continued):

Key Inclusion (Continued):

- Cohort 2 only: Subject must have received prior treatment with JAK-2 inhibitor therapy and meet one of the following criteria (a or b):
 - a. Prior treatment with JAK-2 inhibitor for at least 12 weeks
 - b. Prior treatment with JAK-2 inhibitor for ≥ 28 days complicated by any of the following:
 - i. Development of red blood cell transfusion requirement (at least 2 units/month for 2 months)

OR

- ii. Grade ≥ 3 adverse events of thrombocytopenia, anemia, hematoma and/or hemorrhage while on JAK-2 inhibitor treatment
- Cohort 3 only: Subject must not have received prior treatment with a JAK-2 or BET inhibitor
- Subject has splenomegaly defined as spleen palpation measurement ≥ 5 cm below costal margin or spleen volume $\geq 450 \text{ cm}^3$ as assessed by MRI/CT
- Cohorts 1b and 3 only: Subject has at least 2 symptoms each with a score \geq 3 or a total score of ≥ 12, as measured by the MFSAF v4.0, on at least 4 out of 7 days during screening, prior to study drug dosing.
- Subject must meet the following laboratory parameters per local laboratory reference range during screening, prior to study drug dosing:
 - Adequate bone marrow reserves; in the absence of growth factors, thrombopoietic factors, or platelet transfusions for at least 14 days:
 - Platelet count $\geq 100 \times 10^9 / L$ (Cohorts 1a, 1b or 3)
 - Platelet count $\geq 75 \times 10^9 / L$ (Cohort 2)
 - ANC > $1 \times 10^{9}/L$
 - Renal function: calculated creatinine clearance ≥ 30 mL/min using the Cockcroft-Gault
 - Hepatic function and enzymes:
 - AST and ALT $\leq 3.0 \times$ the upper normal limit (ULN)

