- A spleen volume increase of $\geq 25\%$ (as assessed by MRI or CT scan) in iv. subjects with a spleen volume assessment prior to the initiation of ruxolitinib.
- c. Prior or current treatment with ruxolitinib for ≥ 28 days with intolerance defined as new RBC transfusion requirement (at least 2 units/month for 2 months) while receiving a total daily ruxolitinib dose of \geq 30 mg but unable to reduce dose further due to lack of efficacy.
- 9. Cohort 1b only: Subjects that are receiving ruxolitinib at the time of screening, must currently be on a stable dose ≥ 10 mg twice daily of ruxolitinib for ≥ 4 weeks prior to the 1st dose of navitoclax.
 - *Note:* Subjects with ruxolitinib dose reductions within 4 weeks prior to study enrollment are considered to be on stable dose if dose of ruxolitinib is unchanged for ≥ 2 weeks prior to Day 1 of navitoclax. The current dose must be ≥ 10 mg twice daily. If the dose reduction was due to thrombocytopenia, platelet counts must be confirmed to be stable by a repeat laboratory test.
- 10. **Cohort 1b only:** Subject must not have received treatment with a BET inhibitor or an alternate JAK-2 inhibitor other than ruxolitinib.
- Cohort 2 only: Subject must have received prior treatment with JAK-2 inhibitor 11. therapy and meet one of the following criteria (a or b):
 - a. Prior treatment with JAK-2 inhibitor for at least 12 weeks
 - b. Prior treatment with JAK-2 inhibitor for ≥ 28 days complicated by any of the following:
 - Development of red blood cell transfusion requirement (at least 2 units/month for 2 months OR
 - Grade ≥ 3 adverse events of thrombocytopenia, anemia, hematoma and/or hemorrhage while on JAK-2 inhibitor treatment

- 12. **Cohort 3 only:** Subject must not have received prior treatment with a JAK-2 or BET inhibitor.
- Subject has splenomegaly defined as a spleen palpation measurement ≥ 5 cm below 13. costal margin or spleen volume $\geq 450 \text{ cm}^3$ as assessed by MRI/CT.
- 14. Cohorts 1b and 3 only: Subject has at least 2 symptoms each with a score \geq 3 or a total score of \geq 12, as measured by the MFSAF v4.0 on at least 4 out of 7 days during screening prior to study drug dosing.
- 15. Subject must meet the following laboratory parameters per local laboratory reference range during screening, prior to study drug dosing:
 - Adequate bone marrow reserve; in the absence of growth factors, thrombopoietic factors, or platelet transfusions for at least 14 days:

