MFSAF v4.0 is a symptom diary in which patients rate the following seven MF symptoms: fatigue, night sweats, abdominal discomfort, pruritus, pain under the ribs on the left side, early satiety, and bone pain on a daily basis using a scale from 0 (absent) to 10 (worst imaginable). The TSS reflects the sum of the scores of these symptoms, for a maximum possible score of 70 (ie, most severe symptom experience).

Subjects will be provided with a handheld device at the Screening Visit and should complete the Myelofibrosis Symptom Assessment Form (MFSAF) v4.0 at home around the same time each day during the screening period. All data entered on the device will be immediately stored to the device itself and transmitted to a central server. The investigator and delegated staff will be able to access all uploaded subject entered data via a password protected website, up until the generation, receipt, and confirmation of the study archive.

For subjects enrolled in Cohorts 1b and 3, the investigator/designee should ensure that the subject has completed the MFSAF v4.0 questionnaire on at least 4 of the 7 days prior to the first dose of navitoclax (Day 1). If the investigator believes that the MFSAF v4.0 score on the day before the first dose of navitoclax (Day 1) is not an accurate reflection of the subject's mean symptom score, then the investigator can use the available data to calculate a mean weekly score to determine eligibility. Subjects should then continue to complete the MFSAF daily on the handheld device from the Day 1 visit through the Week 36 visit around the same time each day.

EORTC QLQ-C30 Version 3

Health-related quality of life (HRQoL) and symptoms will also be assessed with the EORTC QLQ-C30 version 3. The EORTC QLQ-C30 is a 30-item subject self-report questionnaire composed of both multi-item and single domains/scales, including five functional scales (physical, role, emotional, social, and cognitive), three symptom scales (fatigue, nausea and vomiting, and pain), a global health status/quality of life scale, and

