#### 7.2 Additional Baseline Definitions

#### 7.2.1 Baseline TSS Value

The total symptom score (TSS) will be measured by Myelofibrosis Symptom Assessment Form (MFSAF) v4.0. The daily TSS scores will be calculated by summing up scores from 7 items of the MFSAF. All seven items must be completed for a daily TSS score to be computed. The worst (highest) daily TSS score will be considered as the daily TSS for a day when multiple responses on the same day were reported.

For subjects who enrolled under Study Protocol Amendment 7 or earlier version, the baseline TSS will be calculated by averaging all available daily TSS score collected up to the first date of study treatment (including the first date of study treatment).

For subjects who enrolled under Study Protocol Amendment 8 or later version, the baseline TSS score is defined as the average of the daily TSS score within 7 days before the first date of study treatment (not including the first date of study treatment). At least 4 days of scores are required to calculate the baseline TSS score. If a subject does not have at least 4 days of scores before the first date of the study treatment (not including the first date of study treatment), the subject will not have a baseline TSS score (see detail in Appendix C).

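### Protocol Section 5.3.1.1 lets an investigator-calculated weekly mean with no cut-off decide symptom eligibility, while inclusion criterion 14 counts days, so Cohorts 1b and 3 have two entry rules that can disagree in either direction.

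*Protocol*

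**What the plan says.** Criterion 14 (Protocol 5.2.1, Cohorts 1b and 3 only) opens "Subject has at least 2 symptoms each with a score" of 3 or more, offers a total of 12 or more as the alternative, and ends "as measured by the MFSAF v4.0 on at least 4 out of 7 days during screening prior to study drug dosing". The Synopsis repeats it with the day count set off by commas: "on at least 4 out of 7 days during screening, prior to study drug dosing".

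Protocol 5.3.1.1, under MFSAF Version 4.0, describes something different. It first asks the site to make sure the diary was filled in on four or more of the seven days before first dose. That is a completion requirement and says nothing about the level of the scores. It then sets a condition: "If the investigator believes that the MFSAF v4.0 score on the day before the first dose of navitoclax (Day 1) is not an accurate reflection". Where that condition holds, an average may replace the doubted value: "then the investigator can use the available data to calculate a mean weekly score to determine eligibility". The paragraph does not refer to criterion 14. It gives no cut-off for the mean and does not say whether totals or single items are averaged.

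SAP 7.2.1 fixes a third quantity. For subjects enrolled under Amendment 8 or later, "the baseline TSS score is defined as the average of the daily TSS score within 7 days before the first date of study treatment", with at least four days of scores required.

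**The concern.** Criterion 14 counts days at or above a threshold. Section 5.3.1.1 averages scores, and its wording suggests that the day-before-dosing score is the starting basis. A count of days and a mean are different statistics and need not agree. A site that follows 5.3.1.1 can therefore enrol a subject who fails criterion 14, or turn away one who meets it, and nothing says which text governs.

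At stake is the make-up of Cohorts 1b and 3, and with it the reading of TSS50W24, the secondary endpoint of a 50% fall in total symptom score at Week 24. Criterion 14 is the only stated guarantee that these subjects had symptoms at entry.

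A lesser point concerns the window. Criterion 14 accepts seven days during a screening period of up to 28 days, whereas the SAP baseline uses the seven days before Day 1. The qualifying week and the baseline week need not be the same.

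**Working it through.** No sample size or precision figure in the documents depends on criterion 14, so there is no stated number to reproduce. The check has two parts.

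**Worked diaries.** There are seven items scored 0 to 10, so the total runs from 0 to 70. A day counts under criterion 14 if at least two items are 3 or more, or if the total is 12 or more. Section 5.3.1.1 gives no cut-off for the mean, so the criterion 14 thresholds are assumed.

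- Diary A: totals 8,8,8,8,20,20,20, with low days four items at 2 and high days four items at 5. A low day has no item at 3 and a total below 12, so it does not count. Qualifying days: 3 of 7, which fails criterion 14. Mean total = (4×8 + 3×20)/7 = 92/7 = 13.1, which passes the mean. The four items each average (4×2 + 3×5)/7 = 23/7 = 3.3, so the item leg passes too.
- Diary B: totals 6,6,6,6,0,0,0, with the 6 made of two items at 3. Qualifying days: 4 of 7, which passes criterion 14. Mean total = 24/7 = 3.4, and the two items average 12/7 = 1.7, so it fails the mean on both legs.
- Diary C, relevant only if the day-before score is itself a test: totals 4,4,4,4,4,4,13. A total of 4 cannot hold two items at 3. Qualifying days: 1 of 7, which fails criterion 14; the last day passes at 13; mean = 37/7 = 5.3.

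A and B suffice to show that the two written rules conflict in both directions.

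**Size, under an assumed model.** The documents give no distribution of daily scores. Assumptions: total-score leg only; daily totals normal, independent, rounded and held within 0 to 70; true mean 8, 10 or 12; day-to-day SD 3, 4 or 6; cut-off 12 for the mean; 400,000 simulated diaries per setting.

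At true mean 10 and SD 4:

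- pass criterion 14 (4 of 7 days): 20.5%
- pass weekly mean: 10.1%
- pass day-before score: 35.3%
- pass weekly mean or day-before score: 39.1%
- pass weekly mean but fail criterion 14: about 1.6%
- pass either alternative but fail criterion 14: 23.6%

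Subjects passing both the mean and criterion 14 are 10.1 − 1.6 = 8.5%. Those passing criterion 14 but failing the mean are 20.5 − 8.5 = 12.0%. In this setting the mean excludes more subjects than it adds.

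Over the nine settings, the share admitted by the weekly mean yet failing criterion 14 is about 0 to 7%. If a day-before score alone also suffices, it is 12 to 24%. Day-to-day correlation lowers the latter: 11 to 20% at lag-1 correlation 0.5, and 9 to 16% at 0.7. At a true mean of 16 with independent days it is about 4% or less, and at 20 at most 0.1%.

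**The case against.** **Criterion 14 might require only that the diary be measured on 4 of 7 days.** The weekly mean would then not contradict it. But the criterion would have no rule for combining days, and the commas in the Synopsis favour the reading that the threshold itself must be met on 4 days. On either reading the text needs repair.

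**The protocol already binds enrolment to all criteria.** Section 5.2 and the Screening text in 5.3.1.1 say so, and SAP Appendix A counts subjects who did not satisfy entry criteria. This limits the damage, but it does not say whether a subject admitted on the weekly mean satisfied the criterion.

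**The windows largely align in practice.** At least seven diary days before Day 1 are provided for, and completion on 4 of the last 7 is required. This stands in part: nothing makes the qualifying week the last one, but the window is a minor issue.

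**Stronger readings a reader might infer, and why they are not supported:**

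- *A single day's score is enough.* Section 5.3.1.1 implies that starting point but ties eligibility expressly only to the weekly mean. It presents the mean as a replacement for an unrepresentative score and does not say that the better of two tests counts. The 12 to 24% rests on that most permissive reading and on true means close to the cut-off.
- *The extra subjects have a baseline below the entry threshold, which makes a 50% fall easy.* Twelve is not the floor of criterion 14. A daily total of 6 qualifies, and Diary B qualifies with a mean of 3.4. Low baselines are permitted by the criterion itself.
- *Totals alone show failure.* They do not: 6,6,6,6,6,6,50 meets criterion 14 on all seven days if each 6 is two items at 3.
- *Investigators will use the discretion to admit patients.* The documents hold no evidence on conduct.

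**Conclusion.** The contradiction is real and rests on the wording alone: a day-count rule in criterion 14 and the Synopsis, and a weekly mean without a cut-off in Section 5.3.1.1. It can admit subjects who fail criterion 14 and exclude subjects who pass it.

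The size is uncertain and probably modest. For the route stated in the protocol, about 0 to 7% would be admitted against criterion 14. This assumes a cut-off of 12, the total-score leg only, independent days, true means of 8 to 12 and SDs of 3 to 6. Larger figures need the implied single-day route, and even those fade for subjects whose usual score is well above 12.

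The consequence is confined to the population of Cohorts 1b and 3 and to TSS50W24, which is estimated descriptively with no formal test. The definition of SVR35W24 and its precision table do not depend on this score. The point merits correction because the repair is cheap; it does not undermine the trial.

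**What to change.** 1. Reconcile the Synopsis, criterion 14 and Section 5.3.1.1 so that one test governs: remove the sentence in 5.3.1.1 that lets a mean determine eligibility, and refer there to criterion 14.
2. Name the seven days in criterion 14 and the Synopsis, preferably the seven days before Day 1, which is the SAP 7.2.1 baseline window.
3. For subjects already enrolled in Cohorts 1b and 3, derive criterion 14 from the stored electronic diary and count failures under the existing entry-criteria category in SAP Appendix A.

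The cost is one wording change and one derived flag from data already held. The downsides are a few more screen failures or recorded deviations and, if the last seven days are used, eligibility that can be confirmed only shortly before dosing. If enrolment has finished, step 3 is the part that still has an effect.
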